## **8.6 Adverse events**

All adverse events will be detailed, as in Appendix G. The total number of SAEs and NSAEs will be reported by allocation and overall with further summaries of this data by type of event, relatedness to study treatment and expectedness also given. The proportion of participants experiencing at least one adverse event which was deemed possibly, probably or definitely related to treatment will be reported by allocation together with odds ratios and risk difference for allocation (and two-sided Wald 95% CIs). The mean, median and mode of the number of adverse events per participant will be presented by allocation.

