## **2. Design**

DISC is a multi-centre, parallel group, individually randomised controlled non-inferiority trial of collagenase injection and manipulation versus limited fasciectomy surgery for the treatment of Dupuytren's contracture. In addition to the main study, DISC contains a qualitative sub study and a photography sub study. This plan outlines the pre-specified analyses of the main trial and the photography sub study. Eligible and consenting patients will be randomised 1:1 to either collagenase injection and manipulation or limited fasciectomy surgery, using a secure randomisation service. Due to the nature of the interventions under investigation, it is not possible to blind clinicians or participants to their treatment allocation. Both treatments should be delivered within 18 weeks of randomisation (as per referral to treatment time), however where possible sites should deliver treatment within 12 weeks of randomisation. Participants will be followed up at 2 and 6 weeks post treatment and 3, 6, 12 and 24 months post treatment. A flow diagram illustrating the flow of participants through the study is presented in Appendix A.

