## 6.7 Adverse Events

An adverse event (AE) is defined as any untoward medical occurrence experienced by any DISC study participant, which may or may not have a causal relationship with the study treatment. An AE is defined as a serious adverse event (SAE) if it fulfils one, or more, of the following criteria;

- Resulted in death
- Was life threatening
- Resulted in inpatient hospitalisation or prolongation of existing hospitalisation
- Resulted in persistent or significant disability or incapacity
- Resulted in congenital anomaly or birth defect
- Required a surgical or medical intervention to treat/prevent any of the above

All SAE/AEs will be reported and followed up using SAE/AE report forms. The following data are collected;

- Whether or not the AE/SAE was a complication associated with the study treatment
- Specific information about the AE/SAE
- Action taken/treatment given
- Date of onset
- Date of remission (if not ongoing)
- Outcome
- Treatment received
- Relationship to study treatment
- Expectedness
- Seriousness

- Details of death
- Follow up details

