#### 8.4.11 Complications

Data pertaining to complications and adverse events related to treatment are collected, in both the investigator completed follow up CRFs and as part of the adverse event reporting. These will be graded according to their severity using an eight level ordinal classification from no complications up to death (Table 4). Grades will be allocated based on the following domains; symptoms, intervention, recovery duration and residual disability. Allocation of a given complication to a particular grade will initially be performed by two observers working independently of one another. A meeting between the two observers will be used to resolve any conflicts in the initial ranking/classification assigned. The justifications for the assignment of a given complication to a particular level will be recorded and will be available for review.

**Table 4:** Ordinal classification used to rank treatment complications;

Level	Definition
None (0)	No complications identified
Technical – not complication (1)	Events related to treatment, but not technically complications (e.g. soft or broken cast, over tight splint)

Very minor (2)	Events related to treatment, but possible to immediately remedy (e.g. removal of retained stich, cast soreness (without pressure sores))
Mild (3)	Events related to treatment, but minor based on symptoms and impact and also reversible
Moderate (4)	Events related to treatment that require treatment/action (and/or have ongoing consequences), but do not require hospitalisation or re-operation (e.g. additional therapy and nurse follow up for stiffness, resolving infection)
Severe (5)	Events related to treatment that require treatment/action (and/or have ongoing consequences), and require hospitalisation or re-operation and may have lasting consequences
Devastating (6)	Events related to treatment that require treatment/action (and/or have significant ongoing consequences), and require hospitalisation or re-operation and have significant lasting consequences (e.g. significant and un-resolving chronic regional pain syndrome)
Death (7)	Death (unexpected in DISC and only allocated as a complication if it is directly attributable to the treatment or intervention (e.g. anaphylactic reaction to administered drug leading to death))

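### Section 8.6 gives a confidence interval only for treatment-related adverse events, and neither counts nor compares participants with an SAE or AE of any cause

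*SAP*

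**What the plan says.** SAP section 8.6 plans the following for adverse events.

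- **Event totals.** "The total number of SAEs and NSAEs will be reported by allocation and overall with further summaries of this data by type of event", and also by relatedness and expectedness.
- **One comparison with intervals.** The proportion of participants with "at least one adverse event which was deemed possibly, probably or definitely related to treatment will be reported by allocation together with odds ratios" and a risk difference, each with a Wald 95% CI.
- **A per-participant description.** "The mean, median and mode of the number of adverse events per participant will be presented by allocation".
- **Listings.** The adverse event tables (the second appendix labelled F, which 8.6 calls Appendix G) list each event with participant ID, allocation, relatedness, expectedness, whether treatment had been received, and time since treatment.

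Collection is wider than the comparison. Section 6.7 defines an adverse event as "any untoward medical occurrence experienced by any DISC study participant, which may or may not have a causal relationship with the study treatment".

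Section 8.4.11 adds a second harms analysis with intervals, based on the worst complication grade. Its source is described thus: "Data pertaining to complications and adverse events related to treatment are collected". In Table 4, grades 1 to 6 are all defined as treatment-related, and death counts only if attributable to treatment.

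On blinding, section 2 states that "it is not possible to blind clinicians or participants to their treatment allocation".

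**The concern.** Relatedness is a judgement made after treatment. In an open-label trial it may be made more readily for one treatment than for the other. If so, the proportion with a related event differs between arms even when the same proportion had an event. Equally, a real excess can shrink to nothing. A comparison of any-cause events does not pass through that judgement, but the SAP plans none at participant level.

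The SAP itself shows that the boundary depends on the procedure. Section 8.4.11 repeats the complications analysis without skin tears at manipulation, because these are often an expected part of that treatment. Section 8.6 has no counterpart to that check.

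For serious events the unit matters too. An arm total adds up events, so several SAEs in one person look the same as SAEs in several people. What is at stake is whether the safety summary of two very different procedures can be read without relying on attribution.

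**Working it through.** **What each planned harms summary covers**

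| Summary | Any cause? | Unit | Interval? |
|---|---|---|---|
| 8.6 related AE | No | Participant | Yes |
| 8.4.11 worst complication | No | Participant | Yes |
| 8.6 SAE and NSAE totals and breakdowns | Yes | Event | No |
| 8.6 mean, median, mode of AEs | Yes | Participant, SAEs not separated | No |
| Event listings | Yes | Event, with ID | No |

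No row is any-cause, at participant level and with an interval. No row gives the number of participants with at least one SAE.

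**Sample size used**

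The SAP states no figure for the adverse-event comparison. Its only sample size is for the primary outcome (section 3: margin 6, SD 22, 90% power, one-sided 2.5%). A noncentral t calculation gives 284 per arm (power 90.05%), or 568 in total, and 568 / 0.80 = 710. Both stated figures reproduce. The illustration uses 710 / 2 = 355 per arm; losses before treatment would reduce this.

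**Spurious difference (all rates assumed)**

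Let p be the true any-AE risk, equal in both arms. Let a1 and a0 be the shares of affected participants who have an event called related.

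- RD = p(a1 − a0)
- SE = √[p1(1 − p1)/355 + p0(1 − p0)/355], with p1 = p·a1 and p0 = p·a0
- P(CI excludes 0) = Φ(|RD|/SE − 1.96) + Φ(−|RD|/SE − 1.96)

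Worked case: p = 0.40, a1 = 0.70, a0 = 0.50. Then p1 = 0.28, p0 = 0.20 and RD = 0.08. SE = √[(0.2016 + 0.1600)/355] = 0.0319. The 95% CI is 1.7 to 14.3 points, and the interval excludes zero in 71% of trials.

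Range with a0 = 50%:

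| True risk, both arms | a1 = 60% | a1 = 70% | a1 = 80% |
|---|---|---|---|
| 20% | RD 2 points; 14% | RD 4; 38% | RD 6; 67% |
| 40% | RD 4; 25% | RD 8; 71% | RD 12; 96% |
| 60% | RD 6; 40% | RD 12; 92% | RD 18; >99% |

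The percentage is the share of trials whose 95% CI excludes zero. An any-AE comparison would stay at 5%.

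**Masked difference (all rates assumed)**

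Take true any-AE risks of 40% and 30%, with attribution shares of 45% and 60%. Related risks are 0.40 × 0.45 = 0.18 and 0.30 × 0.60 = 0.18. The related-event RD is 0 (95% CI −5.7 to 5.7 points). The any-AE RD is 10 points (3.0 to 17.0).

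**Event totals against participants (assumed counts)**

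Suppose 15 participants per arm have an SAE, and in one arm one of them has five. The totals are 14 + 5 = 19 against 15, and 19 / 15 = 1.27: 27% more events among the same number of people.

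**The case against.** The case against is substantial, and much of it limits what can be said.

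- **Other intervals exist.** A reader might infer that every harm-related estimate with an interval depends on attribution. The SAP does not support that. Section 8.4.12 gives odds ratios, risk differences and a hazard ratio for further treatment, and 8.4.10 compares flexion, with no relatedness filter. These are relevant to harm, but they are not any-cause adverse-event comparisons. Section 8.4.11 also gives intervals, but for related events only.
- **Serious events get more than a total.** There are breakdowns and a listing with IDs, in which five SAEs in one person would show as five rows with one ID. Participants could be counted by hand, but no such count or comparison is planned.
- **The assessor is not named.** A reader might infer that unblinded staff judge relatedness. Section 6.7 lists relatedness only as a form field, and the protocol may say who decides. For complications, two observers grade independently and record their reasons, though the SAP does not say whether they are masked.
- **Any-cause counts are not immune.** Reporting itself can differ by arm in an open-label trial. Surgery patients also wait longer for treatment (8.2.1), so counting from randomisation would give unequal time at risk.
- **The rates are invented.** The arithmetic shows that bias is possible, not that it is likely.

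All of this stands as qualification. None of it supplies the missing participant-level comparison.

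**Conclusion.** The gap is real and cheap to close. Section 8.6 contains no contradiction or wrong formula, and no safety decision rule rests on it. It does leave the trial without a count or comparison of participants with at least one SAE, or at least one AE, of any cause, although the data are collected whatever the causality.

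The illustrated bias runs from 2 to 18 risk-difference points, and a true 10-point excess can be hidden. Those sizes rest wholly on assumed event risks and attribution shares and on 355 per arm; the SAP offers nothing to narrow them. A reader might go further and infer that the related-event comparison is invalid or should be demoted. The document does not require that: it answers a legitimate question and can stay where it is.

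**What to change.** In section 8.6, add by allocation the number and proportion of participants with:

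1. at least one SAE of any cause;
2. at least one AE of any cause.

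Give an odds ratio and risk difference with 95% CI for each. Count both over the same window from treatment delivery in the two arms, and show any pre-treatment events separately. The listing already has fields for treatment received and time since treatment. Report these lines alongside the related-event comparison, and put the number of participants affected beside each SAE total.

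The cost is two table lines and one column from data already collected. The drawbacks are that events unconnected with the hand add noise to the second line, and that any-cause reporting may itself differ by arm when allocation is known.

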## **8.7 Photography sub-study analysis**

Participants consenting to participation in the photography sub study will have three sets of joint measurements at baseline and at 3, 6, 12 and 24 months post treatment; measurements obtained using a goniometer, measurements obtained using photographs taken in clinic, and measurements obtained using photographs taken by participants at home. The primary goal of the photography sub study is to assess the agreement between measurements obtained using a goniometer and measurements obtained using the photographs taken by participants at home, in order to determine whether the two methods of measurement might feasibly be used interchangeably. The photography sub study will also include a number of additional analyses investigating agreement between goniometric measurements and measurements obtained using patient photos following treatment, agreement between goniometric

measurements and measurements obtained using photos taken in clinic, and predictors of agreement (image quality and time elapsed between each type of measurement).

### 8.7.1 Primary sub-study analysis

The primary sub-study analysis will investigate the agreement between the mean of the three measurements obtained using goniometer at baseline, and the measurement obtained using patient photographs at baseline (or patient photographs taken prior to treatment if baseline photos are unavailable). We will calculate separate 95% limits of agreement for the MCP and PIP joints of participants' reference digits. A range of plots will be used to assess the extent to which the assumptions of these analyses are met. If there is evidence of a relationship between the differences of the two measurements and their magnitude, then steps will be taken to account for this relationship using regression methods [13]. The calculation of the limits of agreement assumes that the differences are approximately normally distributed. The extent to which this assumption is met will be assessed by inspection of a normal quantile-quantile plot. Should there be extreme departures from normality then a non-parametric approach will be used as described in [13]. The differences between the two types of measurement will be plotted against their average, with the estimated limits of agreement overlaid. The extent to which agreement varies by digit will be investigated by generating separate limits of agreement and plots by digit (little, ring or middle/index/thumb). If feasible, the extent to which agreement varies according to image quality will be investigated by generating separate limits of agreement and plots by image quality category. The extent to which time between measurements explains variation in agreement will be explored by regressing the observed differences on the magnitude of the measurements (i.e. the average of the measurements obtained using each method) and the time elapsed between the two measurements.

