#### **5.6 Joint measurements**

Goniometric measurements are collected and recorded by investigators in clinic. These will be used to assess range of movement (RoM) and recurrence of contracture post treatment. The collection of this data is summarised in Table 1.

**Table 1:** Joint measurement data collection

Measurement type	Baseline	Pre treatment	3 months	6 months	12 months	24 months
Active extension	x	x	x	x	x	x
Flexion	x		x	x	x	x
Passive extension	x	x	x	x	x	x

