### 5.9 Photographs in clinic

Three photographs of participants' hands will be collected at baseline and 3, 6, 12 and 24 months post treatment as follows

- A photograph of the reference hand in extension, taken directly above the hand (anterior view)
- A photograph of the reference hand in extension, taken from the side with the little finger closest to the camera
- A photograph of the reference hand in flexion, taken from the side with the little finger closest to the camera

These images will be used to obtain further measurements of active extension and flexion of the reference digit at each time point. The joint measurements obtained using these images will be used to validate and supplement goniometric measurements and will also be used for secondary analyses in the photography sub study.

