Post-treatment PEM scores (four time points)	Continuous	Percentage disability (0 – 100)	Predictive mean matching (10 nearest neighbours)
Reference joint	Binary	MCP = 0, PIP = 1	N/A (complete)
Baseline PEM score	Continuous	Percentage disability (0 – 100)	Predictive mean matching (10 nearest neighbours)
Treatment delivery PEM score	Continuous	Percentage disability (0 – 100)	Predictive mean matching (10 nearest neighbours)
Baseline URAM score	Continuous	Integer score between 0 and 45	Predictive mean matching (10 nearest neighbours)
Post-treatment URAM scores (four time points)	Continuous	Integer score between 0 and 45	Predictive mean matching (10 nearest neighbours)
Baseline MHQ score	Continuous	Overall MHQ score between 0 and 100	Predictive mean matching (10 nearest neighbours)
Post-treatment MHQ score (two time points)	Continuous	Overall MHQ score between 0 and 100	Predictive mean matching (10 nearest neighbours)
Passive extension of reference joint at baseline	Continuous	Mean of the available passive extension measurements taken of the reference joint at baseline	Linear regression
Passive extension of reference joint at treatment delivery and 3, 6, 12 and 24 months post-treatment	Continuous	Mean of the available passive extension measurements taken of the reference joint at treatment delivery and 3, 6, 12 and 24 months post-treatment	Linear regression
Active extension of reference joint at baseline	Continuous	Mean of the available active extension measurements taken of the reference joint at baseline	Linear regression
Active extension of reference joint at treatment delivery and 3, 6, 12 and 24 months post-treatment	Continuous	Mean of the available active extension measurements taken of the reference joint at treatment delivery and 3, 6, 12 and 24 months post-treatment	Linear regression
Flexion of reference joint at baseline	Continuous	Mean of the available flexion measurements taken of the reference joint at baseline	Linear regression
Flexion of reference joint at treatment delivery and 3, 6, 12 and 24 months post-treatment	Continuous	Mean of the available flexion measurements taken of the reference joint at treatment delivery and 3, 6, 12 and 24 months post-treatment	Linear regression

Crossover	Binary	Did not receive allocated treatment = 0, Received allocated treatment = 1	Logistic regression (with data augmentation if necessary)
Complications	Binary	No complication = 0, Complication = 1	Logistic regression (with data augmentation if necessary)

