### 8.3.2 Other sensitivity analyses of the primary outcome

In addition to the sensitivity analyses investigating the possible influence of missing data, a further three sensitivity analyses will be conducted, investigating the possible influence of differential delay between baseline and treatment delivery in each arm, deviations from the scheduled timing of post-treatment follow ups and an analysis adjusting for additional predictors of disease recurrence. The results of these analyses will be reported in a similar manner to the reporting of the primary analysis (Appendix E-2).

Delay between baseline and treatment delivery differs between the two arms, with participants in the surgery arm generally waiting longer between the two time points. The additional delay in the surgery

arm may lead to greater disease progression by the point of treatment delivery. Hence the baseline measurements in the surgery arm may underestimate severity of disease (at treatment) in comparison to those in the collagenase arm, meaning covariate adjustment using the baseline measurements may lead to a treatment effect estimate which is biased toward zero. Thus the treatment effect estimate from the model adjusting for baseline (as in the primary analysis) may be anti-conservative (in the context of non-inferiority). We will therefore supplement this estimate, with an estimate from a model which adjusts for the PEM measurement taken at treatment delivery (in place of the baseline measurement with all other terms remaining the same as the primary analysis). Any missing treatment delivery PEM scores will be imputed with predicted scores via regression of the observed treatment delivery PEM scores on observed baseline PEM scores and reference joint (MCP or PIP). If the baseline PEM score is also missing then the reference joint strata specific means will be used instead.

To investigate the robustness of the primary analysis to deviations from the scheduled timing of study visits/assessments, the primary analysis models will be refitted using only participants who had PEM scores collected within +/-14 days of the scheduled visit date at 3 and 6 months and within +/-91 days of the scheduled visit date at 12 and 24 months. Any missing baseline PEM scores will be imputed as for the primary analysis.

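### In the primary photography analysis, fallback photographs taken before treatment are compared with baseline goniometry, so for those pairs any true change during the wait counts as disagreement between methods

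*SAP*

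**What the plan says.** Section 8.7.1 sets the goniometer side of the primary sub-study comparison as "the mean of the three measurements obtained using goniometer at baseline". The photograph side is the participant's baseline photograph, "or patient photographs taken prior to treatment if baseline photos are unavailable". No date or window is given for the substitute, and nothing says that the goniometer side changes with it. The section also plans to regress the differences on their magnitude and on the time between the two measurements.

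Table 1 in Section 5.6 marks active and passive extension at both baseline and pre-treatment, but flexion at baseline only. Table 3 in Section 8.3.1 also lists "Active extension of reference joint at treatment delivery and 3, 6, 12 and 24 months post-treatment", but contradicts Table 1 by listing "Flexion of reference joint at treatment delivery and 3, 6, 12 and 24 months post-treatment". Appendix B makes joint measurements mandatory at treatment delivery without separating the types.

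The clinic images are meant to yield "further measurements of active extension and flexion of the reference digit at each time point" (Section 5.9), and Section 5.10 has participants take the same views. Section 2 allows up to 18 weeks from randomisation to treatment.

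**The concern.** Limits of agreement should describe the difference between two methods applied to the same hand in the same state. In a fallback pair the goniometer describes the hand at baseline and the photograph describes it at some later point before treatment.

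The SAP accepts elsewhere that this interval can matter. Section 8.3.2 says that the longer delay in the surgery "arm may lead to greater disease progression by the point of treatment delivery", and plans a sensitivity analysis with the treatment-delivery PEM score for that reason. The sub-study has a repeat extension measurement available and makes no similar provision.

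These limits are the main result on whether home photographs could stand in for clinic goniometry. They also affect how readers take the analyses in Sections 8.4.7 to 8.4.10, where participant photographs fill gaps in goniometry.

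**Working it through.** The sub-study states no sample size, expected agreement or acceptable limit, so there is no figure in the plan to reproduce. The check has two parts.

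**1. Is there a better-timed comparator?**

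- Active extension: yes, at treatment delivery. Table 1 and Table 3 agree.
- Passive extension: also repeated, but Section 5.9 has the photographs yield active extension and flexion, so it is not the matching type.
- Flexion: unclear. Table 1 has no pre-treatment flexion; Table 3 lists it at treatment delivery.
- Number of readings: three at baseline (8.7.1). For treatment delivery, Table 3 refers only to a mean of whatever readings are available. Section 7.2.1 lists a supplementary joint-measurement form at baseline but none at treatment delivery.
- Which comparator is nearer depends on the photograph's date. As an example, a photograph taken 3 weeks after baseline, with treatment at 18 weeks, is 3 weeks from baseline goniometry and 18 − 3 = 15 weeks from the delivery reading.

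**2. How far could the limits move?**

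Let f be the share of fallback pairs, m and s the mean and SD of true change in those pairs (degrees), and σ the SD of the difference between methods when both are applied at the same time. Assume no systematic difference between methods, and change independent of method error. Then

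- bias = f·m
- SD = √(σ² + f·s² + f(1 − f)·m²)
- limits = bias ± 1.96·SD

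All four inputs are assumptions; the SAP gives none of them. With time-matched pairs the limits are ±1.96 × 5 = ±9.8 for σ = 5 and ±1.96 × 8 = ±15.7 for σ = 8.

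| σ | f | m | s | Variance | Bias | Limits | Width ratio |
|---|---|---|---|---|---|---|---|
| 5 | 10% | 2 | 3 | 25 + 0.9 + 0.36 = 26.26 | 0.20 | −9.8 to 10.2 | 1.02 |
| 5 | 25% | 5 | 5 | 25 + 6.25 + 4.69 = 35.94 | 1.25 | −10.5 to 13.0 | 1.20 |
| 5 | 50% | 10 | 8 | 25 + 32 + 25 = 82 | 5.00 | −12.7 to 22.7 | 1.81 |
| 8 | 10% | 2 | 3 | 64 + 0.9 + 0.36 = 65.26 | 0.20 | −15.6 to 16.0 | 1.01 |
| 8 | 25% | 5 | 5 | 64 + 6.25 + 4.69 = 74.94 | 1.25 | −15.7 to 18.2 | 1.08 |
| 8 | 50% | 10 | 8 | 64 + 32 + 25 = 121 | 5.00 | −16.6 to 26.6 | 1.38 |

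If every fallback pair used a same-time reading, m and s would drop out and the limits would return to ±9.8 or ±15.7.

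**The case against.** The main comparison is baseline with baseline, and participants are asked to photograph the hand soon after the baseline visit (Section 5.10). The fallback may be rare. Its effect may be very small, and no acceptability threshold exists for it to cross. Extra spread would tend to make photographs look worse, so it is unlikely to produce a false claim of interchangeability. Elapsed time is a planned predictor of agreement, and the analyses in Section 8.7.2 do not use this fallback. Switching comparator could also mix a mean of three readings with a mean of fewer.

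Most of this stands, and it limits the point. A reader might infer any of the following, which the SAP does not support:

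- That the whole primary analysis is mismatched in time. Only substituted photographs are.
- That the delivery reading is always the closer partner. The substitute is undated and may be nearer baseline.
- That flexion is definitely not measured at treatment delivery. Tables 1 and 3 disagree.
- That the distortion falls mainly on the surgery arm. Surgery participants are expected to wait longer, but nothing says how fallbacks divide between arms.

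What does not stand is that the regression deals with the problem. As written it explores variation in the differences. It does not adjust the limits, and no separate reporting of fallback pairs is planned.

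**Conclusion.** The point holds for fallback pairs only. Where the substitute photograph was taken away from baseline, true change in the joint is counted as disagreement, although an active-extension reading at treatment delivery is scheduled and may be closer in time.

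The size cannot be fixed from the SAP. Over the assumed inputs the limits widen by 1–2% at the low end and by 38% (σ = 8) to 81% (σ = 5) at the high end, with bias from 0.2 to 5 degrees. The high end needs half the pairs to be fallbacks and a mean change of 10 degrees. The SAP says that progression may occur but gives no figure in degrees.

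This concerns the sub-study's primary result. It has no bearing on the trial's primary non-inferiority conclusion. The case for acting is that a pairing rule is cheap and removes the dependence on these unknowns.

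**What to change.** In Section 8.7.1:

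1. Base the primary limits of agreement on pairs matched in time. Pair each photograph, by its actual date, with the nearest goniometric measurement of the same type (active extension with active extension).
2. Report the number of fallback pairs, and give limits with and without them, because the number of goniometer readings at treatment delivery may differ from the three at baseline.
3. Where no time-matched flexion reading exists, keep those pairs out of the primary limits and report them separately.

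Elsewhere in the SAP:

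4. Reconcile Table 1 with Table 3 on whether flexion is measured at treatment delivery.
5. Reconcile Section 7.2.1, which lists five participant photograph sets with none at treatment delivery, with Appendix B, which marks a conditional set there.

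The cost is a wording change, a different merge rule and one extra set of limits, on data already scheduled for collection. The downside is that a few pairs may leave the primary limits or be compared with a mean of fewer readings.
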